7.11.2 Biochemistry

- Frequency of testing: At Screening Visit, T7, T15, End of Treatment Phase Visit or Treatment Failure Visit

Biochemistry profile includes assessment of

Hepatic function indicators: total and direct bilirubin, alkaline phosphatase, aspartate aminotransferase (AST), alanine aminotransferase (ALT), total protein, LDH

Renal function indicators: BUN, creatinine

Electrolytes: sodium, potassium, chloride, calcium and bicarbonate

Other: glucose (random), cholesterol (total)

7.11.3 PK sample for PRO 140

- Frequency of testing: At the T1, T7, T15, EOT and TF visits.

7.11.4 Anti-idiotypic antibodies to PRO 140

- Frequency of sample collection*: At the T1, T7, T15, EOT and TF visits in addition to Treatment Failure Follow-up Visit 1 (TF-FU1) and Non-Treatment Failure Follow-up Visit 2 (NTF-FU2)

***Note:** Sera will be collected from study subjects and stored at -80°C for future analysis.

7.11.5 Serum pregnancy test

- Frequency of testing: At Screening Visit
- Only for female subjects of childbearing potential. Childbearing potential is defined as someone who is not surgically sterile or is not more than one year past complete cessation of menstrual cycles.

7.11.6 Urine pregnancy test

- Frequency of testing: At Treatment Visit 1 prior to first treatment administration
- A urine sample will be collected from female subjects of childbearing potential. This test will be performed at the study site using a commercially available kit.

7.11.7 Plasma HIV-1 RNA level and TruCount T Assay

- Frequency of testing: At SV, Treatment Visits 1, 2, 3, 7, 11, 15, 19 and 23, as well as EOT and TF visits. In addition, blood sample will also be collected at all Treatment Failure Follow-up (TF-FU) Visits or Non-Treatment Failure Follow-up (NTF-FU) Visits.
- To assess antiretroviral therapeutic response to PRO 140

Note: *Plasma HIV-1 RNA level will be measured using Human Immunodeficiency Virus 1 (HIV-1), Quantitative, RNA (Abbott RealTime) test.*

TruCount T Assay includes measurement of Absolute Lymphocytes, CD3 cell count, CD4 cell count, CD8 cell count, CD3%, CD4% and CD8%

7.11.8 HIV-1 Trofile® Assay

- Includes:
 - a. Trofile® RNA Assay
 - b. Trofile® DNA Assay

Trofile® RNA is the primary assay used to assess HIV-1 co-receptor tropism status. However, Trofile® DNA can be used at the discretion of the Investigator when last recorded viral load is less than 1000 copies/mL.

- Frequency of testing: At SV and TF visits

7.11.9 HIV-1 Drug Resistance Assay

- Includes:
 - a. PhenoSense® GT

b. PhenoSense Integrase and GeneSeq Integrase testing

PhenoSense® GT is a combination resistance test for three classes of antiretroviral drugs (i.e., nucleoside/nucleotide, non-nucleoside, and protease inhibitors), that provides both phenotypic and genotypic results from the same blood sample (viral load ≥ 500 copies/ml).

PhenoSense Integrase and GeneSeq Integrase testing will be additionally performed if subject has past exposure to an integrase or in cases where complex drug resistance patterns is known or suspected.

- Frequency of sample collection: At SV, T1, T2, T3, T7, T11, T15, T19, T23 and TF

Samples for PhenoSense® GT (and PhenoSense Integrase and GeneSeq Integrase testing, if collected) during visits T1, T2, T3, T7, T11, T15, T19, and T23 will be stored at Lab and will be analyzed only if subject experiences Treatment Failure.

7.11.10 HIV-1 PhenoSense® Entry assay

- Frequency of testing: At SV and TF visits
- With AMD3100 (CXCR4 inhibitor drug), Maraviroc and PRO 140 (CCR5 inhibitor drugs).

7.11.11 Serum Concentration of ART drugs

- Frequency of sample collection: At Treatment Visits 1, 7, 15, EOT and TF.
- Sample collected at T1 visit is to identify serum concentration for ART drugs (failing regimen) at the time of first study dose while sample collected at T7, T15, EOT and TF visit is to confirm subject compliance to OBT regimen during Part 2 of the Treatment Phase.

7.11.12 Blood sample collection for Exploratory/Confirmatory analysis

- Includes:
 - a. HIV-1 Coreceptor Tropism with Reflex to Ultradeep Sequencing or
 - b. HIV-1 Proviral Tropism

The Quest Diagnostics HIV-1 coreceptor tropism test begins with standard Sanger sequencing of the third variable (V3) loop of the HIV-1 gene, the primary determinant of viral tropism. The next-generation DNA sequencing (ultradeep sequencing [UDS]) is performed if standard sequencing detects only CCR5 virus. HIV-1 Coreceptor Tropism, Proviral DNA test is used when the plasma viral load is < 1000 copies/mL.

- Frequency of testing: At SV and TF visits

7.11.13 Urinalysis

- Frequency of testing: At the Screening Visit, T12, EOT and TF.
- Urine samples will be tested for color, appearance, specific gravity, pH, protein, glucose, occult blood, ketones, leukocyte esterase, nitrite, bilirubin, urobilinogen, and microscopic examination of urine sediment

7.11.14 Coagulation Indices

- Frequency of testing: At the Screening Visit, T12, EOT and TF.
- Prothrombin time (PT) and International Normalized Ratio (INR)

All laboratory reports will be reviewed by the Investigator.

Post-treatment abnormal results that are considered by the Investigator to be clinically significant will be recorded as adverse events. If the Investigator judges it necessary, testing may be repeated in order to make the determination of clinical significance. Validated, quality-controlled laboratory data will be transferred to the main database for analyses.

7.12 INVESTIGATIONAL PRODUCT ADMINISTRATION

Refer to [Section 6.4](#) for details.

7.13 INJECTION SITE REACTION ASSESSMENT

At each treatment visit that occurs at the clinical site, an injection site reaction assessment will be made for the current and previous injection sites. Injection site reaction assessments are recorded by the Investigator (or designee) starting after the first injection is given. Refer to [sections 9.1.8](#) and [16.3](#) for more details.

[figure not shown]
7.14 PAIN ASSESSMENT USING VISUAL ANALOG SCALE (VAS)

Tolerability of repeated subcutaneous administration of PRO 140 is evaluated based on assessment of subject-perceived injection site pain using the Pain Visual Analog Scale (VAS). This assessment will be performed each time subjects arrive to the clinic for the study visit.

Beginning at Treatment Visit 2, subjects will be asked to mark the point that best represents the average pain intensity **over the past week** at the injection site on a horizontal line (100 mm in length) anchored by the following word descriptors at each end, "no pain" on the left side and "pain as bad as it could possibly be" on the right side of the line. The subject marks on the line or by pointing to a position on the line the point that they feel represents their perception of their

pain state. The VAS score is determined by measuring in millimeters from the left-hand end of the line to the point that the patient marks.

Figure 7-1: Visual Analog Scale

8 STATISTICAL CONSIDERATIONS

This section presents general information about statistical considerations and concepts such as statistical power, sample size, and a brief discussion on analysis methodology, as well as some data conventions. Detailed descriptions of the statistical analysis methods and data conventions that will be used in this study will be in a separate document; i.e., the Statistical Analysis Plan (SAP).

8.1 TREATMENT GROUPS

This is an open label study. All eligible subjects will receive study treatment within 6 weeks of Screening Visit, followed by weekly subcutaneous injections of study treatment for up to 24 weeks.

8.2 DESCRIPTION OF STUDY ENDPOINTS

8.2.1 Primary Endpoint

The primary endpoint for this study is proportion of participants with a $\geq 0.5 \log_{10}$ reduction in HIV-1 RNA viral load from baseline to the end of the initial 1-week treatment period.

8.2.2 Secondary Endpoint

The secondary endpoints will be as follows:

1. Proportion of participants with $\geq 1 \log_{10}$ reduction in HIV-1 RNA viral load from baseline to the end of the initial 1-week treatment period
2. Mean change from Baseline in HIV-1 RNA levels (\log_{10} copies/mL) to the end of the initial 1-week treatment period
3. Percentage of participants achieving HIV-1 RNA < 400 copies/mL at week 25
4. Percentage of participants achieving HIV-1 RNA < 50 copies/mL at week 25
5. Mean change from Baseline in HIV-1 RNA levels (\log_{10} copies/mL) at week 25
6. Mean change from Baseline in CD4 cell count at the end of the initial 1-week treatment period
7. Mean change from Baseline in CD4 cell count at week 25

8.2.3 Safety Assessments

Safety measurements will include:

- Emergence of Dual/Mixed (D/M)- and CXCR4-tropic virus in patients who had exclusive CCR5-tropic virus at study entry

- Tolerability of repeated subcutaneous administration of PRO 140 as assessed by study participants (using Visual Analogue Scale) and by investigator-evaluation of injection site reactions
- Frequency of treatment-related adverse events resulting in study drug discontinuation
- Frequency of Grade 3 or 4 adverse events as defined by the DAIDS Adverse Event scale
- Frequency of treatment-emergent serious adverse events

8.3 SAMPLE SIZE DETERMINATION AND RATIONALE

Up to 25 subjects (or any number of subjects that can be enrolled by the time of BLA submission for PRO 140) will be enrolled in this study. The sample size is based on clinical judgement with an intention to supplement the data for the target BLA indication.

8.4 RANDOMIZATION AND BLINDING

No randomization or blinding requirement.

8.5 INTERIM ANALYSIS

No interim analysis planned for this study.

8.6 GENERAL STATISTICAL CONSIDERATIONS

8.6.1 Analysis Populations

8.6.1.1 Intent-to-Treat Population

The Intent-to-Treat (ITT) population is defined as the set of subjects who are enrolled and have received at least one dose of PRO 140.

Subjects who discontinue from the study prior to their first post-baseline assessment will be included in the ITT population and analyzed as non-responders in the primary safety analysis.

8.6.1.2 Per Protocol Population

The Per Protocol (PP) population is defined as the set of subjects who meet the ITT population requirements, and were not associated with a major protocol violation. This population will be identified before the database lock.

8.6.1.3 Safety Population

The Safety population is defined as all subjects who received at least one dose of PRO 140. This population will be used for the analysis of safety parameters.

8.6.2 Statistical Methods

All collected study data will be presented in subject data listings. Statistical analyses will be performed using SAS® for Windows, version 9.4 or later.

A SAP will be developed and approved before the database is locked. The SAP will present the detailed statistical methodology to be used in analyzing the efficacy and safety data from this trial including details of appropriate statistical tests to examine underlying assumptions.

8.6.3 Prognostic Factors/Covariates

There are no pre-planned covariates analyses of the data from this study.

8.6.4 Handling of Missing Data

For the per protocol analysis of efficacy endpoints there will be no imputation of missing data. However, missing data will be imputed using different methods that will be detailed in the SAP for the ITT population of the primary and secondary endpoints.

8.7 DATA SUMMARY

8.7.1 Subject Disposition

The disposition of all subjects who sign an ICF will be provided. The number of subjects screened, received treatment, completed, and discontinued during the study, as well as the reasons for all post treatment discontinuations will be summarized. Disposition and reason for study discontinuation will also be provided as a by-subject listing.

8.7.2 Demographic and Baseline Characteristics

Demographics and baseline characteristics (i.e., Age, Gender, Time since HIV diagnosis, Viral load at Screening Visit, etc.) will be summarized using appropriate descriptive statistics.

Medical history of the subjects will also be provided as a by-subject listing.

8.7.3 Prior and Concomitant Medications

Prior and concomitant medications will be summarized for the Safety population. All prior and concomitant medications recorded in the eCRFs will be coded to generic term and all matching Anatomic Therapeutic Classification (ATC) codes using WHO Drug Summaries will be prepared using the coded terms. All prior and concomitant medications recorded in the eCRFs will also be listed.

8.7.4 Efficacy Analysis

8.7.4.1 Primary Analysis

The primary analysis will be conducted on the ITT population.

All data from the primary and secondary endpoints will be summarized and tabulated according to the variable type:

- Continuous data summaries will include:
Number of observations, mean, standard deviation, median, and minimum and maximum values.
- Categorical data summaries will include:
 - Frequency counts and percentages.

8.7.4.2 Supportive Analysis

To assess the consistency of the Primary Analysis results, supportive analysis will be conducted using the PP population. Statistical methodology for the supportive analyses will be the same as that of the primary analysis, with the exception of the analysis population used.

8.7.5 Safety Analysis

The Safety population will be used for the analysis of safety assessments.

For continuous variables data will be summarized using n, mean, Standard Deviation (SD), minimum and maximum values. For categorical variables data will be summarized using frequency and percentage. No inferential statistics are planned.

8.7.5.1 Adverse Events

Adverse events will be coded using Medical Dictionary for Regulatory Activities (MedDRA). TEAEs are defined as events with an onset on or after the first treatment. TEAEs will be summarized by treatment group, System Organ Class, and preferred term. The following TEAE summaries will be provided:

- TEAEs by severity grade
- TEAEs by relationship to study treatment.

In addition, separate summaries of SAEs, and AEs resulting in discontinuation of study treatment will be presented.

8.7.5.2 Tolerability Assessment

All data from tolerability assessments of repeated subcutaneous administration of PRO 140 as assessed by study participants (using Visual Analogue Scale) and by investigator-evaluation of injection site reactions will be summarized.

8.7.5.3 Clinical Laboratory Data

All laboratory values will be listed. Laboratory measurements will also be summarized.

8.7.5.4 Physical Examination

All physical examination findings will be listed and any abnormality will be summarized.

8.7.5.5 Vital Signs

All vital sign assessment findings will be listed and summarized.

8.7.5.6 ECG Examination

All ECG examination findings will be listed and any abnormality will be summarized.

8.7.5.7 Neurological Assessment

All neurological assessment findings will be listed and any abnormality will be summarized.

9 ADVERSE EVENTS (DEFINITIONS AND REPORTING)

The Investigator is responsible for the detection and documentation of events meeting the criteria and definition of an AE or SAE, as provided in this protocol. During the study when there is a safety evaluation, the Investigator or site staff will be responsible for detecting, documenting, and reporting AEs and SAEs as detailed in this section of the protocol.

9.1 ADVERSE EVENT

An adverse event (AE) is defined as any unfavorable or unintended sign, symptom, or disease that occurs or is reported by the subject to have occurred, or a worsening of a pre-existing condition. An AE may or may not be related to the study treatment.

AEs will be elicited through direct questioning and subject reports. Any abnormalities in visit evaluations, physical examination findings or laboratory results that the Investigator believes are clinically significant to the research subject and that occurred after initiation of the first study treatment will be reported as AEs. Abnormal findings that are NOT clinically significant (NCS) should not be recorded as an AE.

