3.3.2 Exclusion Criteria

Subjects meeting any of the following criteria will be excluded from the study:

1. Documented CXCR4-tropic virus or Dual/Mixed tropic (R5X4) virus as determined by HIV-1 tropism assay

2. Patients with no viable treatment options (i.e., no fully active antiretroviral drug available which can be effectively combined to form a viable new OBT)

3. Any active infection or malignancy requiring acute therapy (with the exception of local cutaneous Kaposi's sarcoma)

Note: Subjects infected by the hepatitis B virus or hepatitis C virus will be eligible for the study if they have no signs of hepatic decompensation and meet the liver function tests eligibility criteria

4. Laboratory test values of \geq grade 3 DAIDS laboratory abnormality with the exception of the absolute CD4+ count criterion of $<200/\text{mm}^3$

5. Females who are pregnant, lactating, or breastfeeding, or who plan to become pregnant during the study

6. Unexplained fever or clinically significant illness within 1 week prior to the first study dose

7. Any vaccination within 2 weeks prior to the first study dose

8. Subjects weighing $<35\text{kg}$

9. History of anaphylaxis to oral or parenteral drugs

10. History of Bleeding Disorder or patients on anti-coagulant therapy

11. Participation in an experimental drug trial(s) within 30 days of the Screening Visit

12. Any known allergy or antibodies to the study drug or excipients

13. Treatment with any of the following:

a. Radiation or cytotoxic chemotherapy with 30 days prior to the screening visit

b. Immunosuppressants within 60 days prior to the screening visit

[figure not shown]
c. Immunomodulating agents (e.g., interleukins, interferons), hydroxyurea, or foscarnet within 60 days prior to the screening visit

d. Oral or parenteral corticosteroids within 30 days prior to the Screening Visit.

Subjects on chronic steroid therapy $>5\text{ mg/day}$ will be excluded with the following exception:

○ Subjects on inhaled, nasal, or topical steroids will not be excluded

[figure not shown]
14. Any other clinical condition that, in the Investigator's judgment, would potentially compromise study compliance or the ability to evaluate safety/efficacy

Figure 3-1: Study Flow Diagram

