5.2.1 Discontinuation of Study Treatment

Discontinuation of study treatment (PRO 140) and continuation of HAART as per standard of care is recommended if:

- Subject experiences treatment failure

Defined in terms of virologic non-response and virologic rebound in the Open-Label Treatment Phase (Part 2) of the study:

(1) Virologic non-response is defined as two consecutive viral load results of:

- $<0.5 \log_{10}$ copies/mL decrease in HIV-1 RNA at Day 7 of Treatment Phase Part 2. [Assessment Timepoint: T3 visit]
- $<1 \log_{10}$ copies/mL decrease in HIV-1 RNA at or after Week 4 of Treatment Phase Part 2 unless HIV-1 RNA <400 copies/mL. [Assessment Timepoint: from T6 up to T25 visit]
- Confirmed plasma HIV-1 RNA levels ≥ 400 copies/mL at Week 24 of Treatment Phase Part 2. [Assessment Timepoint: T25 visit]

(2) Virologic rebound is defined as two consecutive viral load results of:

- $\geq 1.0 \log_{10}$ copies/mL increase in plasma HIV-1 RNA above nadir level* in Treatment Phase Part 2 [Assessment Timepoint: from T3 up to T25 visit] or

**Note: This refers to “Nadir” level in Treatment Phase Part 2 which starts from T2 visit*

- ≥ 400 copies/mL after suppression to <50 copies/mL in Treatment Phase Part 2. [Assessment Timepoint: from T3 up to T25 visit]

Note: Subjects will be allowed to continue PRO 140 with existing OBT regimen while waiting for new regimen to be constructed by the Investigator.

- Develops AIDS-defining conditions as specified in Appendix I ([Section 16.1](#)) under which subject is unable to continue treatment with study drug (PRO 140), or subject require treatment with prohibited concomitant medications.
- Shows signs or symptoms of clinically significant immunosuppression
- Subject or the subject's clinician wishes to adjust OBT (except in the event of toxicity management).
- Subject becomes pregnant.

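### Sections 9.1 and 7.11 do not exempt HIV-1 RNA and CD4 results from adverse event recording, so virologic failures and CD4 falls can enter the AE tables, inconsistently across sites

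*Protocol*

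**What the plan says.** **Recording rule.** Section 9.1 covers "Any abnormalities in visit evaluations, physical examination findings or laboratory results that the Investigator believes are clinically significant to the research subject" and says that those "that occurred after initiation of the first study treatment will be reported as AEs". It adds a filter: "Abnormal findings that are NOT clinically significant (NCS) should not be recorded as an AE". The AE definition in the same section also includes worsening of a condition already present, and HIV infection is not set apart. The closing text of section 7.11, printed under 7.11.14 but opening with a reference to all laboratory reports, says: "Post-treatment abnormal results that are considered by the Investigator to be clinically significant will be recorded as adverse events".

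**What 7.11 contains.** HIV-1 RNA and the TruCount assay, which supplies CD4, are in 7.11.7. Their stated purpose there is to assess response to treatment.

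**Role of these results.** HIV-1 RNA carries the primary endpoint (8.2.1) and several secondary endpoints. CD4 change is a secondary endpoint at one week and at week 25 (8.2.2). HIV-1 RNA also defines treatment failure, which heads the list in section 5.2.1: "Discontinuation of study treatment (PRO 140) and continuation of HAART as per standard of care is recommended if".

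**Where AEs are reported.** Section 8.2.3 lists "Frequency of Grade 3 or 4 adverse events as defined by the DAIDS Adverse Event scale". Section 8.7.5.1 says that "separate summaries of SAEs, and AEs resulting in discontinuation of study treatment will be presented". Section 9.1.2 has the investigator record, for each AE, whether study treatment was discontinued.

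**An exemption that exists elsewhere.** Exclusion criterion 4 (section 3.3.2) bars laboratory values of DAIDS grade 3 or higher, "with the exception of the absolute CD4+ count criterion of" below 200/mm³. Section 9 has no matching rule for values seen on study.

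**The concern.** The same laboratory results serve as efficacy outcomes and, on the wording of 9.1 and 7.11, as potential AEs. A confirmed rebound brings a treatment failure visit with resistance and tropism testing, a change of background regimen (4.3.4) and cessation of PRO 140 (sections 3 and 5.2.1). An investigator who follows the text could hardly call that result clinically insignificant. Another may regard it as plainly an efficacy outcome and record nothing. The protocol supports either practice.

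At stake is what the safety percentages mean. Up to 25 subjects are planned, without a control group, to supplement a licence application (8.3). A few failures recorded as AEs would put lack of efficacy into the AE counts and the discontinuation summary, and CD4 falls could raise the Grade 3-4 frequency. This is a rule for completing the CRF, so an analysis plan written later cannot restore uniform recording.

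**Working it through.** The protocol gives no figure to reproduce. The check is a reading of the text, followed by a scale calculation.

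**Step 1. Is there an exemption?** Sections 7.11.7, 7.11.14, 8.7.5.1, 9.1 and 9.1.2 contain none for HIV-1 RNA or CD4. The only CD4 exemption is in exclusion criterion 4, which governs entry.

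**Step 2. Which results can qualify?** Under 9.1 a result must be judged clinically significant and must have arisen, or worsened, after the first dose.
- *Rebound* (a confirmed rise of at least 1.0 log10 above nadir, or at least 400 copies/mL after suppression below 50) arises on treatment and is the clearest candidate.
- *Non-response* describes viremia that persists. Subjects enter with at least 400 copies/mL (3.3.1), rechecked at T0 (4.2), and conditions that emerge before T1 are medical history (7.4). Non-response need be neither new nor worse.
- *CD4 falls* qualify only if new or worse. Criterion 4 lets subjects enter below 200/mm³.

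**Step 3. Which tables are exposed?**

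| Table | Virologic failure | CD4 fall |
|---|---|---|
| AE counts | Yes, if recorded | Yes, if recorded |
| AEs resulting in discontinuation (8.7.5.1) | Yes, if recorded and coded as stopping PRO 140 | Not by itself; 5.2.1 lists no CD4 criterion |
| Treatment-related AEs resulting in discontinuation (8.2.3) | Only if also judged treatment-related | Not by itself |
| Grade 3-4 AEs (8.2.3) | Depends on the grade assigned | Yes; criterion 4 implies that a count below 200/mm³ reaches grade 3 or higher |

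**Step 4. A second route.** Section 7.6 says that the indication for a concomitant medication started during the study should be considered an AE, and it applies no test of clinical significance. Whether antiretrovirals count as concomitant medications there is unclear. If they do, a regimen change after failure, or the start of the optimized background regimen itself, could make viremia an AE.

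**Step 5. Scale.** Let N be the number treated, k the number of treatment failures, and s the share of them coded as AEs leading to discontinuation.

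- Addition to the 8.7.5.1 summary = 100 x k x s / N percentage points.
- At N = 25: 100 / 25 = 4, so the addition is 4 x k x s.
- At s = 0 it is 0; at s = 1 it is 4k.

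The protocol gives neither k nor s. As an assumption only, failure in 10% to 40% of subjects means k = 0.10 x 25 = 2.5 to 0.40 x 25 = 10. The addition is then 0 to 4 x 2.5 = 10 points at the lower rate and 0 to 4 x 10 = 40 points at the upper rate, depending on s.

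**The case against.** A reader might infer that every treatment failure and every CD4 fall is counted again as an AE and as an AE that stopped PRO 140. The protocol does not support that.

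- Recording depends on the investigator's judgement and on onset or worsening after the first dose. Persistent entry viremia and a CD4 count already low at entry need not qualify.
- A CD4 fall is not a stopping criterion. The nearest item in 5.2.1 is signs or symptoms of clinically significant immunosuppression.
- Treatment failure has its own pathway: failures go to the TF visit and other discontinuations to the EOT visit (4.3). Under 5.2.1, PRO 140 may continue while a new regimen is built, and the action taken is assessed for each AE. Failure on the T25 criterion comes at the last planned dose, with little or nothing left to discontinue.
- The discontinuation endpoint in 8.2.3 counts treatment-related AEs only.
- A reader of the results could separate virologic events without a comparator, because AEs are tabulated by preferred term (8.7.5.1), data are listed by subject (8.6.2), and reasons for discontinuation are summarised and listed (8.7.1).

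All of this stands. It limits how much double counting can occur and shows that the damage can be traced. It does not supply the missing exemption or make sites record alike, and the summary in 8.7.5.1 is not limited to related events.

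An exemption covering every virology assay would also go too far. Emergence of dual/mixed- or CXCR4-tropic virus is a listed safety assessment (8.2.3). Drug resistance is a named risk to subjects (1.6.1.1) and has no dedicated summary in section 8.

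**Conclusion.** The point holds in limited form. Sections 9.1 and 7.11 state a mandatory recording rule that, followed as written, allows efficacy failure into the AE data and leaves the extent to each site. The tables exposed are the AE counts, the unrestricted discontinuation summary in 8.7.5.1 (through failures that stop PRO 140) and the Grade 3-4 frequency (through CD4 falls that are new or worse).

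The effect on the discontinuation summary is 4 x k x s points at N = 25, anywhere from 0 to 4k. It would be tempting to say that a true toxicity discontinuation rate of 0/25 would appear as 10% to 40%. That is a worst case: it needs the assumed failure rate and s = 1, and the text requires neither. The size also rests on N = 25, whereas section 8.3 allows any number enrolled by the time of the licence application. The correction is worth making because it is cheap and must be in place when sites record the data.

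**What to change.** 1. In 9.1 and the closing text of 7.11, state that plasma HIV-1 RNA and CD4 values, and virologic failure without clinical signs, are efficacy outcomes and are not in themselves AEs. State also that any resulting clinical event (for example an AIDS-defining condition), and any event meeting a seriousness criterion, is recorded as usual.
2. Align 7.6, so that a change of antiretroviral regimen does not by itself create an AE through its indication.
3. Report stops for treatment failure under disposition (8.7.1) and keep them out of the 8.7.5.1 summary of AEs resulting in discontinuation.
4. Leave tropism and drug-resistance findings outside the exemption.

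The cost is minor rewording and a CRF completion note. HIV-1 RNA, CD4 and reasons for discontinuation are already collected and reported elsewhere, so no data are lost. No dose or stopping rule changes.
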